Comparing Effectiveness of Duloxetine and Desipramine in Patients With Chronic Pain: A Pragmatic Trial Using Point of Care Randomization

Statistical Analysis Plan

NCT03548454

Revised March 28, 2025

Statistical Analysis. The initial sample size calculation determined that 107 participants per group would provide 90% power to detect a one-unit between-group difference in the NRS pain score ($SD=2.25$) at $\alpha=0.05$. However, the study was prematurely stopped due to most referred patients having prior experience with duloxetine or, less frequently, desipramine. As a result, we enrolled 38 patients in the desipramine group and 48 in the duloxetine group. With this sample size, we could detect a difference of 1.37–1.58 in NRS pain reduction with 80–90% power.

Participants were eligible if they completed at least one survey before being assigned a study medication and at least one follow-up survey. The baseline assessment was defined as the most recent survey before treatment assignment. Participants without follow-up surveys or those lost to follow-up were excluded. The primary analysis followed modified intention-to-treat (ITT) principles. However, within the first day of treatment assignment, five individuals switched from desipramine to duloxetine. To account for these switches, a per-protocol (PP) analysis was conducted, categorizing individuals based on the medication they took. For consistency, survey data (research and clinical surveys) were evaluated up to 52 weeks post-baseline when available.

Baseline demographic and clinical characteristics were summarized using three comparative analyses. First, a “per-protocol” approach was applied to compare demographic and clinical characteristics between the desipramine and duloxetine groups. Second, differences were assessed between participants who completed the full course of medication and those who discontinued early. Third, participants who achieved a clinically meaningful ($\geq 30\%$) pain reduction were compared to those who did not. Categorical variables were analyzed using Pearson’s Chi-square or Fisher’s Exact tests, while continuous variables were assessed using t-tests or Mann-Whitney U tests depending on normality.

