Longitudinal changes in pain intensity, physical function, and psychological function were analyzed using linear mixed-effects models (LMMs). Dependent variables included pain intensity (average and worst), PROMIS Pain Interference, PROMIS Anxiety, PROMIS Depression, and PROMIS Physical Function (Upper Extremity, Mobility, and Composite) scores. The primary independent variables were medication group (desipramine vs. duloxetine) and its interaction with time (weeks since baseline) to assess differential treatment effects. Baseline pain intensity was included as a covariate. A random intercept for each participant accounted for within-subject correlations. Various model structures were evaluated using Akaike Information Criterion and Bayesian Information Criterion, with final models selected based on model fit and diagnostic assessments. Model fit was evaluated using residual plots, Q-Q plots, histograms, and Variance Inflation Factor analyses. Bonferroni correction was applied to account for multiple comparisons. LOESS (Locally Estimated Scatterplot Smoothing) predicted values with 95% confidence intervals were plotted to visualize longitudinal trends stratified by medication group.

Kaplan-Meier survival analysis was used to evaluate medication adherence over time, conducted separately for both the intention-to-treat and per-protocol analyses. Time to discontinuation was calculated as the number of days between treatment initiation and discontinuation. Participants who completed the full course of medication were censored at the maximum observed follow-up duration. Kaplan-Meier survival curves were generated for each medication group, and the log-rank test was used to compare groups with 95% confidence intervals. A Kaplan-Meier survival analysis was also conducted to compare the time to achieving a $\geq 30\%$ reduction in average pain intensity from baseline between medication groups. A binary indicator variable was created to determine whether a participant met the pain reduction threshold at any follow-up point, with time-to-event defined as the earliest occurrence of this reduction. Participants who did not achieve the threshold were censored at 52 weeks. Kaplan-Meier survival curves were plotted separately for desipramine and duloxetine, with the log-rank test used for group comparisons.

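### The SAP drops participants lost after randomisation, and its adherence Kaplan-Meier has a censoring rule only for completers, so reported discontinuation can be biased in either direction

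*SAP*

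**What the plan says.** The analysis population is set in the second paragraph of the SAP's Statistical Analysis: "Participants were eligible if they completed at least one survey before being assigned a study medication and at least one follow-up survey". The exclusion follows: "Participants without follow-up surveys or those lost to follow-up were excluded". The label is then given: "The primary analysis followed modified intention-to-treat (ITT) principles". The SAP does not define loss to follow-up, count the exclusions in either arm, or say which analyses the exclusion covers.

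The adherence Kaplan-Meier is described later in the SAP as "conducted separately for both the intention-to-treat and per-protocol analyses", this time without the word modified. On event time it says "Time to discontinuation was calculated as the number of days between treatment initiation and discontinuation". Its one censoring rule is "Participants who completed the full course of medication were censored at the maximum observed follow-up duration", and it does not say whether that maximum is the participant's own or the study's. Nothing covers a participant whose follow-up ends with neither completion nor a recorded stop. The 52-week censoring rule in the same paragraph belongs to the separate curve for time to 30% pain reduction.

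Protocol 1.a names the comparison of compliance as a purpose of the trial. Protocol 2.a collects compliance by monthly survey, takes other medication use from health records, and lets treatment run on only while the patient tolerates it and wants it. The protocol gives no censoring or missing-data rule.

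**The concern.** Selecting participants on what happens after randomisation can undo the comparability that randomisation gave. For a time-to-discontinuation curve it is also unnecessary, because censoring exists to use the time such people did contribute. Here the outcome and the exclusion may be linked. Treatment is open label, a patient may leave because the drug did not suit, and compliance is reported through the same surveys that define follow-up. People who stop answering are therefore those whose drug status is least known.

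Either reading of the SAP leaves a problem. If the exclusion applies to the adherence curve, the curve describes only those who stayed in contact. If the intention-to-treat label means that these people are kept, their censoring time is undefined and the curve cannot be reproduced. At stake is the compliance comparison. The final SAP analysis, which relates completion or early stopping to pain response, uses the same classification.

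**Working it through.** **Inputs.** From the SAP: 38 and 48 enrolled, SD 2.25, alpha 0.05 (two-sided assumed). Every loss and discontinuation rate below is an assumption, since the documents give none.

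**1. The SAP's own figures.** n per group = 2 × (1.960 + 1.282)² × 2.25² / 1² = 106.4, so 107. Detectable difference = (1.960 + z) × 2.25 × √(1/38 + 1/48), which is 1.37 for z = 0.842 (80% power) and 1.58 for z = 1.282 (90%). Both reproduce. The SAP states no figure for loss or discontinuation.

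**2. One arm, true 6-month discontinuation 40%, 20% of participants lost.**

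- *A. All lost had just stopped, with no record of it.* Half of all stops (0.20/0.40) go unrecorded. Excluded: (0.40 − 0.20)/0.80 = 25.0%. Censored at last contact: 1 − 0.60^0.5 = 22.5%. Still on drug: 20.0%. Counted as stopped: 40.0%.
- *B. All lost were still on drug to the end.* Excluded: 0.40/0.80 = 50.0%. Censored at last contact, with loss times uniform: 45.2% (simulation, 2,000,000 participants). Still on drug: 40.0%. Counted as stopped: 60.0%.
- *C. Loss unrelated to stopping, constant hazards.* Stopping hazard a = −ln 0.60 = 0.511. Loss hazard m = 0.291 makes the share lost before any stop equal 20%. Recorded stops: a/(a+m) × (1 − exp(−(a+m))) = 35.1%. Dropping only those lost before a recorded stop gives 0.351/0.80 = 43.9%. Dropping everyone ever lost gives 40.0%, because those left are a random subset. Censored at last contact: 40.0%. Still on drug: 35.1%. Counted as stopped: 35.1 + 20.0 = 55.1%.

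| Scenario (truth 40%) | Excluded | Last contact | Still on drug | Counted as stopped |
|---|---|---|---|---|
| A. Lost had stopped | 25.0% | 22.5% | 20.0% | 40.0% |
| B. Lost were on drug | 50.0% | 45.2% | 40.0% | 60.0% |
| C. Unrelated | 40.0% or 43.9% | 40.0% | 35.1% | 55.1% |

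The last two columns contain 40% in every row. The pair formed by last contact and counted as stopped misses it in row B.

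**3. Two arms.**

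- *Equal loss.* Take true 40% v 60% with 20% lost in each arm. If all lost had stopped, exclusion gives 25% v (0.60 − 0.20)/0.80 = 50%, a gap of 25 points instead of 20. If loss is unrelated and only those lost before a recorded stop are dropped, it gives 43.9% v 0.519/0.80 = 64.9%, a gap of 21.0.
- *Unequal loss.* Take true 50% in both arms (19 of 38, 24 of 48), with 8 and 5 excluded, of whom a share p had stopped. The reported rates are (19 − 8p)/30 and (24 − 5p)/43:

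| p | Desipramine | Duloxetine | Difference (points) |
|---|---|---|---|
| 0.25 | 56.7% | 52.9% | +3.8 |
| 0.50 | 50.0% | 50.0% | 0 |
| 0.75 | 43.3% | 47.1% | −3.8 |
| 1.00 | 36.7% | 44.2% | −7.5 |

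The standard error of such a difference is about √(0.25/30 + 0.25/43) = 0.119, or 12 points.

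**4. Detectable difference, only if 38 and 48 are counts before exclusion.** At 34/43 (about 10% loss) the range becomes 1.45–1.67. At 30/38 (about 20% loss) it becomes 1.54–1.78.

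**The case against.** **The exclusion is stated generally, so there may be nobody left to censor.** It comes before any analysis, and the SAP sorts participants into completers and early stoppers with no third class. This is a fair reading. It settles the missing censoring rule only by confirming the exclusion, which is the more serious problem.

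**Exclusion need not bias anything.** This stands. A reader might infer that dropping lost participants always distorts the curve, or always inflates discontinuation when loss is unrelated to stopping. Neither follows from the documents. Row C gives 40.0% when everyone ever lost is dropped. The 43.9% needs the narrower rule of dropping only those lost before a recorded stop, and the SAP does not state that rule.

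**Censoring at last contact is no cure.** This also stands. If loss follows stopping, it does slightly worse than exclusion (22.5% v 25.0%), so it needs bounds on both sides.

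**Those with no follow-up survey add little.** They would be censored near day 0 unless health records show their drug status. This is true, and it limits how far the main curve would move.

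**The illustrated differences between arms are small against a standard error of about 12 points, and all loss rates are assumed.** This is true as well. Few losses would mean little bias, but the SAP does not let a reader check.

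**Conclusion.** The point holds and should be fixed; confidence is moderate. The SAP removes participants for post-randomisation events, and for its adherence curve it says neither whether they are kept nor when they would be censored. The bias can run either way: 25.0% to 50.0% for a true 40%, if 20% are lost. It can also be nil. The actual size and direction cannot be found without losses by arm. Equal loss in both arms changes the gap little unless loss is tied to stopping.

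Two stronger inferences are not supported. One is that the pain models discard partial followers. One follow-up survey suffices for entry and "survey data (research and clinical surveys) were evaluated up to 52 weeks post-baseline when available", so on the natural reading such people are in. They drop out only if loss to follow-up also covers people who returned some surveys. The other is that 1.37–1.58 is wrong. It is correct for 38 and 48 analysed. The SAP says "we enrolled 38 patients in the desipramine group and 48 in the duloxetine group" without saying whether that is before or after exclusion.

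**What to change.** 1. Strike the loss-to-follow-up limb of the exclusion sentence. Anyone with a baseline survey and any follow-up survey then contributes all available surveys to the mixed models, by randomised arm.
2. Run the intention-to-treat adherence Kaplan-Meier on all randomised participants who started treatment, by randomised arm. Known stops are events. Completers are censored at their own last follow-up. All others are censored at the last date on which surveys or health records show their drug status. Use the same censoring for the per-protocol curve.
3. Add two sensitivity runs as bounds: all lost counted as stopped at last contact, and all lost counted as still on drug to the end of follow-up. State that last-contact censoring assumes loss is unrelated to stopping.
4. Report randomised, never-started, excluded and analysed numbers by arm. Say whether 38 and 48 are before or after exclusion, and restate 1.37–1.58 only if they are before.

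The cost is a few SAP sentences, re-run adherence curves and two sensitivity runs. The mixed models need re-running only if partial followers had been removed. The reported range for discontinuation may widen.

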2. STUDY PROCEDURES

a. Procedures

Study Design: We will conduct a prospective open label randomized trial comparing effectiveness of duloxetine and desipramine.

Randomization (research): After obtaining research informed consent, the participants are going to be randomized by the treating pain provider using point of care randomization during the clinic visit. Point of care randomization will be done through Collaborative

Health Outcomes Information Registry (CHOIR) using computer generated random numbers.

Intervention: (standard of care) The participants are going to receive either duloxetine or desipramine. Duloxetine will be started at 20 mg per day. It will be increased to 40 mg per day at the beginning of week two, and then to 60 mg per day at the beginning of week three. Desipramine will be started at 25 mg per day. It will be increased to 50 mg per day at the beginning of week two, and then to 75 mg per day at the beginning of week three. These treatments will be continued for at least 6 months provided that the patients can tolerate the side effects and are willing to continue the treatment. Further titration of doses based on participants' tolerance and response is allowed based on clinical decision of the treating pain provider. Concomitant use of other analgesics or pain medications as well as pain interventions are also allowed.

Data collection: (standard of care and research) The participants are going to receive monthly electronic surveys which are already part of their routine clinical care. These surveys are going to be abbreviated to include average and worst Numerical Rating Scale (NRS) of pain; National Institute of Health (NIH) Patient Reported Outcomes Measurement Information System (PROMIS) measures for function, depression and pain interference; and questions about medication compliance, dose and adverse events. Data about use of other analgesics and medications, and pain interventions will also be recorded at these intervals from participants' electronic health records. If the participants do not complete the surveys within five days of receipt of the survey link, they will be contacted to be reminded of the survey. We will also record participants' baseline characteristics including age, sex, main pain diagnosis, other pain diagnoses, psychological comorbidities, medical comorbidities, medication use, and education.

b. Procedure Risks

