Cost of the study medication will be borne by the participants and/or insurance company as part of standard of care. The study itself does not incur any cost in addition to standard of care.

m. **Planned Duration of the Study**

We estimate the study to be completed in 5 years as below:

1. Enrollment: 48 months
2. Follow up for last enrolled patient: 6 months
3. Data analysis and reporting the results: 6 months

7. **RISKS**

a. **Potential Risks**

i. **Investigational devices**

None

ii. **Investigational drugs**

None

iii. **Commercially available drugs, biologics, reagents or chemicals**

Potential adverse events are based on package insert approved by United States Food and Drug Administration:

Duloxetine

Reactions are categorized by body system according to the following definitions: frequent adverse reactions are those occurring in at least 1/100 patients; infrequent

adverse reactions are those occurring in 1/100 to 1/1000 patients; rare reactions are those occurring in fewer than 1/1000 patients.

Cardiac Disorders — Frequent: palpitations; Infrequent: myocardial infarction and tachycardia.

Ear and Labyrinth Disorders — Frequent: vertigo; Infrequent: ear pain and tinnitus.

Endocrine Disorders — Infrequent: hypothyroidism.

Eye Disorders — Frequent: vision blurred; Infrequent: diplopia and visual disturbance.

Gastrointestinal Disorders — Frequent: flatulence; Infrequent: eructation, gastritis, halitosis, and stomatitis; Rare: gastric ulcer, hematochezia, and melena.

General Disorders and Administration Site Conditions — Frequent: chills/rigors; Infrequent: feeling abnormal, feeling hot and/or cold, malaise, and thirst; Rare: gait disturbance.

Infections and Infestations — Infrequent: gastroenteritis and laryngitis.

Investigations — Frequent: weight increased; Infrequent: blood cholesterol increased.

Metabolism and Nutrition Disorders — Infrequent: dehydration and hyperlipidemia; Rare: dyslipidemia.

Musculoskeletal and Connective Tissue Disorders — Frequent: musculoskeletal pain; Infrequent: muscle tightness and muscle twitching.

Nervous System Disorders — Frequent: dysgeusia, lethargy, and paresthesia/hypoesthesia; Infrequent: disturbance in attention, dyskinesia, myoclonus, and poor quality sleep; Rare: dysarthria.

Psychiatric Disorders — Frequent: abnormal dreams and sleep disorder; Infrequent: apathy, bruxism, disorientation/confusional state, irritability, mood swings, and suicide attempt; Rare: completed suicide.

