The study will terminate at the completion of follow-up for last patient enrolled. Study medication will be stopped if the participant decides to discontinue the medication. Since the medications used are part of standard clinical care that the patients receive in our clinic, the participants can continue the medication after the completion of the study if they would like to.

e. Data Safety Monitoring Plan (DSMC)

i. Data and/or events subject to review

The treatments in the study are not different from routine clinical practice; therefore, adverse events will be monitored as a part of participants' clinical care by their clinic providers. Protocol Director (PD) will monitor for protocol deviations.

ii. Person(s) responsible for Data and Safety Monitoring

Data and safety will be monitored by investigators and PD.

iii. Frequency of DSMB meetings

N/A

iv. Specific triggers or stopping rules

N/A

v. Will the Protocol Director be the only monitoring entity? (Y/N)

Yes

f. Risks to Special Populations

N/A

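### The SAP uses surveys to 52 weeks where they exist, twice the only follow-up length in the protocol, with no 26-week analysis and no count of late contributors

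*SAP*

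**What the plan says.** **SAP, Statistical Analysis.** On the window: "survey data (research and clinical surveys) were evaluated up to 52 weeks post-baseline when available". The only reason offered is consistency. The analysis set needs one survey before assignment and at least one after it, and "Participants without follow-up surveys or those lost to follow-up were excluded"; the SAP does not say by which week a patient counts as lost. The main model terms are "medication group (desipramine vs. duloxetine) and its interaction with time (weeks since baseline) to assess differential treatment effects", with a random intercept per participant. In the analysis of time to a 30% pain reduction, every patient who never reaches the threshold is censored at week 52. No analysis limited to 26 weeks is described, and no count of contributors by week or arm.

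**Protocol.** Section 6.m (Planned Duration) gives "Follow up for last enrolled patient: 6 months". Section 7.d (Study Conclusion) adds "The study will terminate at the completion of follow-up for last patient enrolled". Section 2.a (Procedures) says "These treatments will be continued for at least 6 months", subject to tolerance and willingness, and "The participants are going to receive monthly electronic surveys which are already part of their routine clinical care". It gives no last survey month. The protocol names no 52-week assessment and no primary time point.

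**The concern.** A 52-week window is twice the 6 months in the protocol, and the second half is filled with whatever surveys exist. Continuing to answer surveys is something that happens after randomisation. It may depend on pain course, tolerability or staying in care, and this may differ between the two drugs.

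That would matter little if late surveys carried little weight. In a model where the arms may diverge with time in weeks, they carry a lot, because observations far from the average time dominate a slope. The treatment-by-time result could then rest on a small and possibly unrepresentative part of each arm, and a reader could not tell, because the counts are not planned for reporting.

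The responder curve has a related problem. Patients with late surveys get more chances to meet the threshold, while patients whose surveys have stopped stay in the risk set to week 52 as if observed.

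**Working it through.** **1. The plan's own figures.** Inputs from the SAP: difference 1, SD 2.25, alpha 0.05 (taken as two-sided), arms of 38 and 48.
- Planned size: 2 × 2.25² × (1.960 + 1.282)² / 1² ≈ 106.4, so 107 per group, as stated.
- Detectable difference: 2.25 × √(1/38 + 1/48) = 0.4886. Times (1.960 + 0.842) this is 1.37 at 80% power; times (1.960 + 1.282) it is 1.58 at 90%. Both match.

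These figures compare two means and do not depend on the window, so they neither support nor contradict 52 weeks.

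**2. Window.** 52 / 26 = 2.0.

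**3. Slope information per patient.** With a random intercept and linear time, one patient's information on the slope is proportional to the sum of squares of the survey times about their mean. The month is 52/12 = 4.333 weeks, and 4.333² = 18.78.
- Months 1–6: 17.5 × 18.78 = 328.6 weeks².
- Months 1–12: 143 × 18.78 = 2,685.2 weeks². Ratio r = 8.17.
- Months 1–6 plus one survey at week 39 (month 9): (172 − 30²/7) × 18.78 = 43.43 × 18.78 = 815.5 weeks². Ratio r = 2.48.

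**4. Share from patients with late surveys.** Let a fraction f have later surveys and the rest months 1–6 only. The fraction f is not in the documents and is assumed. The share from these patients is f·r / (1 − f + f·r). This includes their first six months. The share from the late surveys alone is f(r − 1) / (1 + f(r − 1)). In each range the low end is one survey at week 39 and the high end is six late monthly surveys.

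| f (of 86 enrolled) | Share from these patients | Share added by late surveys alone |
|---|---|---|
| 10% (about 9) | 22–48% | 13–42% |
| 20% (about 17) | 38–67% | 23–59% |
| 30% (about 26) | 52–78% | 31–68% |

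For example, with f = 0.3 and r = 8.17: 2.451 / (0.7 + 2.451) = 0.78. These patients pass half of the slope information at f = 1/(1 + r): about 11% with six late surveys and about 29% with one at week 39. In this set-up the within-patient correlation does not change the per-patient ratio.

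**5. Responder analysis.** A non-achiever whose last survey is at week 26 is censored at week 52. So 52 − 26 = 26 of the 52 weeks at risk, half, are unobserved. Such patients keep the risk set too large, which lowers the estimated cumulative response late in the curve. If surveys stop at different times in the two arms, the log-rank comparison is affected too.

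**The case against.** The strongest reply is that the protocol does not cap follow-up at 6 months for each patient. The figure is for the last enrolled patient in a 48-month enrolment, treatment has a minimum and no maximum, and monthly surveys have no stated end. People enrolled earlier could be followed longer within the protocol. This stands, so the 52-week window is not a breach. But the protocol does not plan observation to week 52 for everyone, which a common window needs if it is to be complete.

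Second, a likelihood-based mixed model uses all available surveys and tolerates missingness that depends on observed scores. That also stands, provided the model is right. Bias needs late response to depend on unobserved outcomes, or a misspecified time trend or covariance. The SAP compares model structures by information criteria, but does not say whether random slopes or curved trends were among them.

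Third, surveys go out by electronic link, with a reminder after five days. The documents do not make completion depend on attending the clinic, so it cannot be assumed that only attenders have late data.

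A reader might also infer that the longer window by itself inflates the false-positive rate of the group-by-time test. If late response is unrelated to pain course, such inflation comes mainly from leaving out a random slope when slopes vary. That is a separate matter. Large inflation from selection needs response linked to course differently in the two arms, and nothing in the documents indicates this.

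**Conclusion.** The point holds as a risk that the plan leaves unexamined. The SAP's window is twice the protocol's only stated follow-up, late surveys enter as they happen to exist, and there is neither a 26-week analysis nor a count of late contributors. If 10–30% of patients have late surveys, they could supply between 22% and 78% of the slope information. This rests on an assumed fraction, linear time, and complete monthly surveys to month 6. It applies to the group-by-time term and not in the same way to the group term.

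A reader might go further and infer that a self-selected minority drives the longitudinal results, or that the randomised comparison is lost. The documents do not support either: they give no counts by week and no reasons for late response. The censoring rule needs no such assumption. As written, it counts unobserved time as event-free.

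**What to change.** - Run the mixed models and the time-to-30%-reduction analysis with a 26-week window as the main analysis. The protocol names no primary time point, so this is a choice, but it matches the protocol's stated follow-up.
- In the responder analysis, censor non-achievers at their last survey. Shortening the window alone does not help patients whose surveys stop before week 26.
- Keep the 52-week analysis with clinical surveys as a labelled sensitivity analysis.
- Report by arm how many patients contribute surveys after week 26.

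**Cost.** New SAP wording and a rerun on existing data. The main analysis loses longer-term information and some precision. Under the assumptions above, the standard error of the slope at 26 weeks is √(1 + f(r − 1)) times that at 52 weeks, from √1.148 = 1.07 (10%, one late survey) to √3.151 = 1.78 (30%, six late surveys).

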6. PARTICIPANT POPULATION

a. Planned Enrollment

Accepting type I error of 0.05 with 90% power, we will require 107 participants per group to detect one unit between-group difference in NRS pain scale. We are proposing a more conservative (larger) sample size to: (1) preserve power if the effect size is underestimated secondary to low medication adherence; and (2) preserve power for our subgroup analyses. We will therefore add 50% to our sample size to a total of 160 patients in each arm. Correlation between repeated measure will decrease variance and increase the power of the proposed study.

b. Age, Gender, and Ethnic Background

Men and women of any ethnic background who are 18 years old or above will be enrolled.

c. Vulnerable Populations

We will not enroll potentially vulnerable subjects.

d. Rationale for Exclusion of Certain Populations

We are studying the comparative effectiveness of these two medications in adults. Study of chronic pain in children is beyond the scope of our study.

e. Stanford Populations

Not applicable

f. Healthy Volunteers

Not applicable

g. Recruitment Details

All adult patients with chronic pain receiving care from Stanford Pain Management Center will be assessed for eligibility by their treating pain physician during each clinical visit. If eligible, the treating pain physician will go through the oral consent script. If the patient consents to participate, he/she will be randomized to receiving either duloxetine or desipramine. Open label prescription will be then sent to participants' pharmacy.

h. Eligibility Criteria

i. Inclusion Criteria

1. Age of 18 years old or above
2. Persistent pain for more than 3 months
3. Candidate for treatment by anti-depressant based on treating pain provider

ii. Exclusion Criteria

1. Prior failure of duloxetine and/or desipramine (patients who have failed other TCAs or SNRIs can be considered for the trial based on the reason for previous medication failure)
2. Contraindication to taking duloxetine or desipramine
3. Patient refusal

i. **Screening Procedures**

We do not collect any PHI prior to enrollment.

j. **Participation in Multiple Protocols**

Participants will be asked if they are enrolled in any other research study.

k. **Payments to Participants**

Participants will not receive any payment for taking part in this study.

l. **Costs to Participants**

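### Apart from baseline pain, the SAP relates baseline characteristics to pain relief only through an unadjusted 30% responder split, which has less power than the NRS mixed model already planned

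*SAP*

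**What the plan says.** The Statistical Analysis section of the SAP lists three comparisons of baseline characteristics and presents them as summaries. In the third, patients with a clinically meaningful (at least 30%) "pain reduction were compared to those who did not. Categorical variables were analyzed using" chi-square or Fisher tests, and continuous variables by t or Mann-Whitney tests. Each characteristic is tested on its own, without adjustment.

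The mixed-model paragraph keeps the outcome on its own scale: "Dependent variables included pain intensity (average and worst"), followed by the PROMIS scores. The listed predictors are medication group, its interaction with time in weeks, and baseline pain intensity as a covariate. No other baseline characteristic appears.

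The Kaplan-Meier paragraph gives the only explicit rule for who counts as a responder: "A binary indicator variable was created to determine whether a participant met the pain reduction threshold at any follow-up point". The paragraph on the third comparison does not say which survey or surveys decide response there.

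On size, the protocol (section 6a) says "We will therefore add 50% to our sample size to a total of 160 patients in each arm", partly to preserve power for subgroup analyses. The SAP reports that "we enrolled 38 patients in the desipramine group and 48 in the duloxetine group".

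**The concern.** A patient whose score goes from 6 to 1 and one whose score goes from 6 to 4 both count as responders. A patient who goes from 6 to 5 is grouped with one whose pain got worse. Tests on such a split use less of the data than tests on the score itself. These tests also ignore baseline pain, although the 30% rule is relative to baseline.

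What is at stake is the reading of the responder table. A characteristic that goes with a real difference in pain can appear as no difference between responders and non-responders, and the tests give no effect in NRS points. A model that would do better on both counts is already in the SAP.

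**Working it through.** **The plan's own figures.** The SAP says "107 participants per group would provide 90% power to detect a one-unit between-group difference in the NRS pain score", with SD 2.25 and alpha 0.05. Two-sided: n = 2 × (1.960 + 1.282)² × 2.25² / 1² = 2 × 10.51 × 5.0625 = 106.4, so 107 per group. For 38 and 48 patients, the detectable difference is (1.960 + z) × 2.25 × √(1/38 + 1/48) = (1.960 + z) × 0.4886. This gives 1.37 for 80% power (z = 0.842) and 1.58 for 90% (z = 1.282). Both match the SAP.

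**Inputs for the check.**
- From the documents: N = 38 + 48 = 86, SD 2.25, and a 1-point difference, borrowed from the sizing of the drug contrast.
- Assumed, because the documents give no value: mean baseline 6, mean drop 1, within-patient correlation 0.5 or 0.7, and a characteristic split 50/50. Scores are whole numbers from 0 to 10.
- The number analysed may be below 86, because patients without follow-up surveys are excluded and their number is not given.

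**Adjusted analysis, one survey, by hand.** The residual SD is 2.25 × √(1 − r²), and the standard error for 43 against 43 is that SD × √(2/43) = SD × 0.2157.
- r = 0.5: SD 1.949, SE 0.420, 1/0.420 = 2.38, and 2.38 − 1.96 = 0.42, so power is about 66%.
- r = 0.7: SD 1.607, SE 0.347, 1/0.347 = 2.89, and 2.89 − 1.96 = 0.93, so power is about 82%.

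Simulation with rounded, bounded scores gives 63% and 79%, slightly lower as expected.

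**Simulated power, two-sided 0.05.** The adjusted analysis regresses mean follow-up NRS on the characteristic and baseline NRS, as a stand-in for the mixed model. A responder is a patient with any follow-up score at or below 0.7 × baseline.

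| Surveys | Correlation | Adjusted NRS | Responder chi-square | Loss (points) |
|---|---|---|---|---|
| 1 | 0.5 | 63% | 44% | 19 |
| 1 | 0.7 | 79% | 60% | 19 |
| 3 | 0.5 | 86% | 56% | 30 |
| 3 | 0.7 | 94% | 73% | 21 |
| 6 | 0.5 | 92% | 54% | 38 |
| 6 | 0.7 | 97% | 75% | 22 |

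Separate runs differ by a few points. Type I error was about 5% for both methods.

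**What the loss consists of.**
- One survey, neither analysis adjusted: uncut percent change has 54% power against 42% for the split (correlation 0.5), and 71% against 57% (correlation 0.7). The cut alone therefore costs about 12 to 14 points.
- One survey, both adjusted (correlation 0.5): 63% against 43% for a baseline-adjusted logistic model, or 20 points. Adjusting the binary analysis does not recover the loss.
- Six surveys, correlation 0.5, in a separate run: adjusted mean 93%, the 30% cut applied to the mean 69%, any-time rule 57%. Of the 36 points lost, 69 − 57 = 12 come from the any-time rule.

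**Check by formula.** Cutting a normal outcome at response rate p multiplies the noncentrality by k = φ(z_p)/√(p(1 − p)), and power becomes Φ(k × (1.960 + z) − 1.960). Starting from 80% power:
- p = 50%: k = 0.798, power 61%, loss 19.
- p = 30%: k = 0.759, power 57%, loss 23.
- p = 12%: k = 0.616, power 41%, loss 39.

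For a single cut, a loss near 40 thus needs a response rate near 12% (or 88%).

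**Less favourable settings.** With one survey and wide variation in true change (SD 1.5), losses started at about 13 points. In one setting with a 0.5-point association, power was 36% against 22%, a loss of 14. Where both analyses are weak, the gap is smaller still. For 0.5 point, one survey and r = 0.5, 0.5/0.420 = 1.19 gives about 22%, and k = 0.759 brings it to about 15%.

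**The case against.** The strongest reply is that the SAP calls these comparisons summaries. No hypothesis or power claim is attached to them, and a responder profile answers its own question: who reaches relief that the SAP regards as clinically meaningful. That is a good reason to keep the table. It is a weaker defence of the p-values, because the SAP does test the differences and offers no other analysis of these characteristics.

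The size of the loss is also open to challenge. The documents give no response rate, baseline mean, correlation or expected association, and the comparison above combines three things: the cut, the missing baseline adjustment and the handling of repeated surveys. This stands, and the figures must be read as conditional on the assumptions. Still, the adjusted full-scale analysis had more power in every non-null setting that was run.

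A reader might go further in four ways that the documents do not support:
- That the loss is a fixed 17 to 40 points. The upper end requires many surveys and the any-time rule, which the SAP states for the Kaplan-Meier analysis, or an extreme response rate.
- That stopping at 86 of 320 (2 × 160) patients causes the loss. At a given starting power, the loss barely depends on N. The small N lowers the power of both analyses.
- That the drug comparison is weakened. The mixed models keep NRS continuous.
- That the full-scale model would reliably find a 1-point association. Its power with one survey is 63-79% under the main assumptions, and lower when true change varies widely.

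**Conclusion.** The point holds as a modest, inexpensive improvement to an exploratory analysis. The third comparison uses a less informative method than one already in the SAP. Under the main assumptions the cost is about 19 points of power with one survey. It is about 13 to 15 points when true change varies widely with one survey, or in the half-point setting with 36% against 22%, and less where both analyses have little power. It nears 40 points only with many surveys and an any-time response rule. The direction is well supported. The exact size is not, because it rests on inputs that the documents do not give.

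The comparison pools the two arms. Improving it would therefore not supply the analysis in the protocol's Objectives (section 1b) of which patients respond differently to the two drugs.

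**What to change.** For the third comparison, enter each baseline characteristic, one at a time, in the planned mixed model of average NRS, adjusted for baseline NRS and medication group. Report its coefficient in NRS points with a 95% confidence interval, labelled exploratory. Keep the 30% responder table as description, without p-values, and state which survey or surveys define response in it.

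The cost is a revised SAP paragraph and a few extra runs of a model already being fitted, with no new data. The small downside is that the inferential result is in NRS points rather than as a responder profile. The descriptive table still shows that profile.
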